**Table 2 Composition of VLA2001 (booster vaccination)**

Active substance	
SARS-CoV-2 inactivated:	Antigen Units/dose antigen dose level equivalent to high dose
Excipients and buffer components	
Aluminium Hydroxide	0.5 mg Al 3+ /dose
CpG 1018	1 mg/dose
Dulbecco's Phosphate Buffered Saline (DPBS) 	
rHA	≤25 µg/dose

## 12.2 IMP Labelling and Packaging

Packaging and labelling of IMP is performed by Almac. Labels will be written in accordance to local law. Valneva will provide one kit containing one vial of VLA2001 and one vial of CpG.

Booster Phase:

Packaging and labelling of IMP is performed by a central manufacturing organization located in the UK (Almac). Labels will be written in accordance to local law. Valneva will provide one kit containing one multi-dose vial of VLA2001.

## 12.3 IMP Storage, Dispensing and Accountability

### 12.3.1 IMP Storage

The IMP should be stored in a refrigerator at +2 to +8°C in a room with access limited to study personnel. Temperature monitoring systems will be used.

**PLEASE DO NOT FREEZE THE VACCINE!**

### **12.3.2 Dispensing and Accountability of Investigational Medicinal Product**

A drug shipment log will be kept current by the site, detailing the date and quantity of IMP received from and returned to the Sponsor. In addition, a current drug dispensing log has to be maintained, detailing the dates and quantities of IMP administered to each Participant. This documentation will be available to the designated CRA to verify drug accountability during the study and to perform overall drug accountability.

Any unused IMP and empty vials will be accounted for and returned to the Sponsor.

Details of IMP handling, including the procedure for Booster Phase are described in the updated study-specific IMP manual.

## **13. STUDY PROCEDURES**

### **13.1 Informed Consent and Enrolment**

Any healthy volunteer who provides informed consent (i.e., signs and dates the informed consent form) is considered enrolled in the study.

The Investigator will inform the Participant about the procedures, risks and benefits of the study. Fully informed, written consent must be obtained from each Participant prior to any assessment being performed. It is important that the Participant is allowed sufficient time to decide on his/her participation in the study.

### **13.2 Participant Identification Code**

At Visit 0, a 10-digit Participant identification code will be assigned to each Participant. The first four digits are the product identifier (e.g. 2001 for this product) provided by the Sponsor. The fifth digit is the study identifier (i.e. 2001-1 for this phase I/II study); the sixth and seventh digit is the site identification number (i.e. 2001-1-01). The last three digits are assigned in ascending order as the Participants are enrolled (i.e., signing the informed consent form, e.g. 2001-1-01-001).

### **13.3 Investigational Treatment**

#### **13.3.1 Description of Treatment**

The vaccination schedule consists of two doses of VLA2001 for each study Participant, administered by intramuscular (IM) injection in the deltoid region of non-dominant arm preferably 21 days apart, on Day 1 and Day 22 [Low dose, Medium dose, High dose].

Booster Phase:

The booster vaccination will be administered IM in the deltoid region of the non-dominant arm; please refer to the updated study-specific IMP manual.

#### **13.3.2 Vaccine Preparation and Administration**

Primary immunization:

One part of the vaccine (labelled VLA2001) will be presented as a liquid formulation containing aluminium hydroxide in glass vials at three dose levels (each vial is pre-filled with 0.4ml) and has to be mixed bedside with CpG 1018 (0.2ml) prior to vaccination (volume for administration is 0.5ml).

Preparation of IMP will be done according to the following procedure:

1. CAUTION: Preservatives, antiseptics, detergents, and other anti-viral substances may inactivate the vaccine. Use only sterile syringes that are free of preservatives, antiseptics, detergents or other anti-viral substances for injection of VLA2001.
2. The VLA2001 glass vial and CpG vials should be removed from the fridge (2-8°) and allowed to reach room temperature before administration
3. The VLA2001 and CpG vials should be gently swirled (5 to 10 seconds) to obtain a homogeneous suspension (no vortex or shaking);
4. The VLA2001 and CpG vials should be inspected visually for any foreign particulate matter and/or variation in physical appearance (e.g. discoloration) prior to withdrawal of the appropriate volume into a syringe. Vials found to contain foreign particulate matter, to be discolored or to leak must be discarded and may not be used; the Sponsor must be informed immediately of such events.
5. Withdraw 0.2ml CpG 1018 with a syringe (the prefilled volume in the CpG vials is approximately 0.7ml). Transfer the 0.2ml CpG 1018 into the VLA2001 vial, the resulting volume is 0.6ml.
6. The mixed vaccine vial should be gently swirled (5 to 10 seconds) to obtain a homogeneous suspension (no vortex or shaking).
7. Take a new needle and withdraw the injection volume of 0.5 mL. The injection site should be prepared according to standard clinical procedures.
8. Injection of 0.5ml mixed vaccine intramuscularly into deltoid region of non-dominant arm by study staff as soon as possible.
9. The used vials and syringes should be kept within the empty kits for drug accountability purposes. Used needles should be disposed in accordance with local requirements.

Under no circumstances should the VLA2001 vaccine be administered intravascularly, as this could lead to hypersensitivity reactions such as shock.

#### Booster Phase:

For the Booster Phase there will be no bed-side mixing necessary. VLA2001 will be provided in multi-dose vials to the study sites where each multi-dose vial will have a unique kit number. In addition, the site will receive unlabelled syringes together with an aspiration and an administration needle and specific syringe labels. Once the pharmacist gets the treatment for a participant, they will retrieve 0.5 mL from the respective multi-dose vial with a syringe. Immediately afterwards this syringe will be labelled with a syringe label (participant identifiers will be added manually on the label). With this process the identification of and allocation of the syringe to a specific multi-dose vial and participant is ensured.

The details of the procedure for Booster Phase are described in the updated IMP manual.

**Anaphylaxis or other possible severe acute, post-vaccination adverse reactions to vaccines, including VLA2001 vaccine, are very rare, but can occur. Therefore, appropriate emergency equipment and medication as well as adequately trained personnel must be on site whenever a vaccination is performed.**

### **13.3.3 Post- Vaccination Observation**

The first Participant of a sentinel dosing group will be observed for 3 hours at the study site following vaccination; all remaining 4 Participants of the sentinel dosing group will be observed for 60 minutes (see Section 10.1) at the study site. All remaining 135 Participant in the randomized and blinded part of the study will be observed at the study site for 30 minutes after each vaccination. This is in order to provide appropriate emergency treatment should this be necessary. In addition, vital signs including pulse rate and blood pressure while seated and at rest will be measured prior to discharge. Any injection site and systemic reactions will be recorded.

#### **Booster Phase:**

For the Booster vaccination, participants should be observed in the clinic for 30 minutes after administration.

Prior to leaving the study site, the Participant will be instructed how to complete the respective electronic diary for documentation of AEs (for further information see Section 15.3), will be given a digital thermometer for measuring oral body temperature and a measuring device for assessing injection site reactions (at the vaccination visit only).

### **13.4 Screening and Study Visits**

The overall study design is illustrated in Section 22.1. Please refer to the Schedule of Study Procedures and Assessments in section 22.2 and section 22.3 (specific to the Booster Phase), for the timings of all procedures to be carried out during the study.

#### **Please note:**

##### **Study Changes in Response to the COVID-19 Pandemic Situation**

Authorities worldwide have issued guidance for Industry, Investigators, and Institutional Review Boards on conducting clinical studies during the COVID-19 pandemic.

Competent health authorities and agencies, including the FDA, the MHRA\* and the HRA\*\*, support the implementation of remote activities to ensure continuation of study activities should the COVID 19 situation limit/forbid access to clinical sites.

Valneva will continuously monitor and evaluate the development of the COVID-19 pandemic in the area of study sites to determine if any measures should be implemented to mitigate undue risks to the Participants or in response to local governmental recommendations.

Such measures can include (but not limited to):

- remote monitoring,
- switching in-person visits to telephone call and/or home visits (including appropriate documentation of the phone call/home visit),
- sending of 'Dear Investigator' Letters to inform investigator sites of changes to trial conduct
- self-isolation of trial Participants as a precaution or as a result of confirmed infection, limiting or inhibiting the required clinical trial activities.

Explicit instructions from Valneva and CRO as to what can be accessed where, will be available and communicated in a timely manner to ensure fulfilment of protocol activities during the trial.

Trial participants will be consented to any identifiers leaving the site and be assured that their confidentiality will be protected.

Furthermore, care will be taken that no extra burdens are placed on investigators and site staff around scanning and uploading many documents.

*The safety of the Participants participating in the trial remains our priority.*

\*MHRA Guidance. (see literature)

### **13.4.1 Unscheduled Visit**

An unscheduled visit can be held at any time during the study if deemed necessary by the Investigator (e.g. follow-up on unexpected AEs or SAEs) or the DSMB. Assessments performed at an unscheduled visit will be at the Investigator's or DSMB's discretion. Unscheduled visits and any procedures/assessments performed during such a visit (e.g. physical examination, laboratory test) should be documented in the source data and the eCRF.

In any case a phone call will only take place if a) data are not being entered; b) grade 3 events are reported, c) if a serious AE is reported via the diary, d) if Participants indicate symptoms towards potential COVID-19 infection.

### 13.4.2 Early Termination Visit

Participants who terminate participation or who are withdrawn from the study prematurely will undergo investigations during an ET visit, if possible. Every effort should be made to have discontinued Participants complete the study ET Visit (see Table 3).

**Table 3 Study VLA2001-201 Study Visit Schedule – Early Termination**

TIME	ACTION
unscheduled	
 
1. Review/Collect Participant diary (Section 15.3)
 
2. AE/AESI/SAE documentation (Section 15.2)
 
3. Concomitant medication (Section 15.4)
 
4. Symptom-driven physical examination and Vital Signs (Section 15.6 and 15.5)
 
5. Blood drawa:               
 
a. Immunogenicity evaluation (Section 14)
 
b. Clinical chemistry, haematology, coagulation assessments (Section 15.7)
 
 
 
6. Urine samples:               
 
a. Urine pregnancy test (if applicable)b
 
b. Urinalysis (Section 15.7)
 
 
 
7. Documentation of reason for early termination
 

AE=adverse event; AESI=adverse event of special interest; SAE=serious adverse event

a The following amounts of blood will be drawn: HIV/HBsAg/HCV screening – 3 mL; serum pregnancy test – 3.5 mL; immunogenicity – 15 mL; clinical chemistry – 7.5 mL; haematology – 5 mL; coagulation – 3 mL.

b A pregnancy test will be performed on all female Participants of child bearing potential at screening (serum pregnancy test), and prior to each vaccination and upon study completion (urine pregnancy test).

If an ET Visit is not possible, a follow-up safety phone call should be made as soon as possible after termination to capture at least concomitant medications and solicited and unsolicited AEs since the last study visit.

The reason for early termination should be clarified in as much detail as possible. If an AE was the reason for early study termination, details of the specific AE(s) should be captured (see Section 11.6). The reason for discontinuation will be recorded on the eCRF, and data collected up to the time of discontinuation will be used in the analysis and included in the clinical study report.

In the event of Participant discontinuation due to an AE, clinical and/or laboratory investigations that are beyond the scope of the required study observations/assessments may be performed as part of the evaluation of the event. These investigations will take place under the direction of the Investigator in consultation with the Sponsor, and the details of the outcome may be reported to the appropriate regulatory authorities by the Sponsor.

### **13.5 Procedures for Monitoring Participant Compliance**

In general, study procedures are to be performed under the supervision of the Investigator or designee at the study site. Participant compliance will be monitored by reviewing the Participant's entries in the e-Diary.

## **14. ASSESSMENT OF IMMUNOGENICITY**

All serum samples obtained for the determination of neutralizing antibodies and IgG antibodies against SARS-CoV-2 will be handled according to the procedures supplied to each investigative site for the preparation, storage and shipment of samples (refer to Laboratory Manual). Immunogenicity samples will be collected from all Participants at the time points indicated in section 22.2 and 22.3. Each clinical study site will be responsible for the separation of serum from whole blood samples and the safe and controlled storage of serum samples prior to shipment to the central laboratory.

Immunogenicity sample (10ml) will be drawn for SARS-CoV-2-specific neutralizing antibody titre evaluation and ELISA antibody titre evaluation.

Serum samples to measure SARS-CoV-2 neutralizing antibody levels will be collected from Participants on Day 1 (prior vaccination), Day 8, Day 22 (prior vaccination), Day 36, Day 106 and Day 208. An authorized laboratory will measure neutralizing antibodies to SARS-CoV-2 using wild-type virus neutralizing assay. In addition to the functional assays, samples will be analysed for IgG against SARS-CoV-2 by ELISA.

The cell-mediated immune response (T-cell response) will be assessed on Day 1, Day 36 and Day 208 by characterizing PBMCs; methods may include T-cell ELISpot assays to SARS-CoV-2 antigens.

Booster Phase:

During the Booster Phase, a blood sample (10 ml) will be collected at Visit 7 (before vaccination), Visit 8 and Visit 9, to measure SARS-CoV-2-specific neutralizing antibody titre and ELISA antibody titre.

Similarly, cell-mediated immune response (T-cell response) will be assessed by characterizing PBMCs at Visit 7 and Visit 8.

More details about the Booster Phase assessments can be found in section 22.3.

At the end of the study, results of immunogenicity assessments will be provided to the Investigator.

## 14.1 Additional Testing Procedures

Instructions for obtaining and processing saliva sampling are provided in the Laboratory Manual.

Self-swabbing samples will be assessed by validated assays for the detection of SARS-CoV-2.

Samples obtained in this study may, in addition to its use for assessment of SARS-CoV-2 specific antibody and cellular immune responses, also be used for further development of the vaccine, including but not limited to the following assays:

- Development of additional neutralization assays (e.g. pseudovirion neutralization assay)
- Detection of antibodies by enzyme linked immunosorbent assay (ELISA) against different SARS-CoV-2 antigens
- Detection of cellular immune responses using different test methods (e.g. ELISpot, intracellular cytokine staining)
- Clinical diagnostic work-up.

Such development may occur at laboratories other than the central analytical laboratory used for this study.

A blood sample for use in passive transfer studies will be collected to support the establishment of a robust clinical endpoint for identification of neutralizing antibody levels associated with protection from COVID-19. These samples may also be used for the preparation of assay controls.

## **15. ASSESSMENT OF SAFETY**

### **15.1 Definitions**

#### **15.1.1 Adverse Events**

An AE is defined as any untoward medical occurrence in a Participant administered an investigational product that does not necessarily have a causal relationship with the treatment. All new abnormalities or any exacerbation in intensity or frequency (worsening) of a pre-existing condition during or after vaccination must be documented as AEs.

#### **15.1.2 Serious Adverse Event**

A SAE is defined as any untoward medical occurrence that at any dose meets one or more of the following criteria:

- Outcome is fatal/results in death (including foetal death).
- Is life-threatening – defined as an event in which the Participant was, in the judgment of the Investigator, at risk of death at the time of the event; it does not refer to an event that hypothetically might have caused death had it been more severe.
- Requires inpatient hospitalisation or results in prolongation of an existing hospitalisation.
- Results in persistent or significant disability/incapacity (i.e., a substantial disruption of a person's ability to conduct normal life functions).
- Results in congenital anomaly/birth defect.
- Is a medically important condition – a medical event that may not be immediately life-threatening or result in death or require hospitalisation but may jeopardize the Participant or may require medical or surgical intervention to prevent one of the other outcomes listed in the definitions above. This definition also applies to progression of disease leading to a serious outcome.

In case of hospitalisation or prolonged hospitalisation for diagnostic or elective medical procedures that were planned prior to vaccination to treat a pre-existing condition that did not change in severity, neither the condition leading to the hospitalisation or prolonged hospitalisation, nor the actual medical procedure need to be reported as an SAE. In this case, the underlying diagnosis or condition should be reported in the medical history section of the eCRF and the corresponding medical procedure should be documented as a comment to the underlying diagnosis or condition in the medical history section of the eCRF.

The Sponsor will classify the SAEs as either expected or unexpected:

**Expected:** An AE that is listed in the current Investigator's Brochure (IB)

**Unexpected:** An AE that is not listed in the current IB, or it differs because of greater severity or greater specificity

**For the purpose of this study, AEs graded as potentially life-threatening (Grade 4) (see Section 15.2.3 for solicited AEs) will be reported as SAEs.**

### **15.1.3 Adverse Events of Special Interest**

An AESI (serious or non-serious) is an event of scientific and medical concern specific to the Sponsor's product. Please refer to Sections 15.10 and 22.5, where symptoms/illnesses considered as an AESI for this study are described.

### **15.1.4 Medically-Attended Adverse Event**

All AEs where Participants are seeking medical care (i.e. doctor's office, emergency service, hospital, but not including use of self-medication).

### **15.1.5 Pre-existing Diseases**

Pre-existing diseases that are present before entry into the study, that are described in the medical history, and that manifest with the same severity, frequency, or duration after vaccine exposure, will not be recorded as AEs. Furthermore, routine health checks required due to pre-existing diseases will not be recorded. However, when there is an increase in the severity of a pre-existing disease, the event must be described on the AE CRF page.

### **15.1.6 Untoward Medical Occurrences Not Considered Adverse Events**

Each untoward medical occurrence experienced before vaccine exposure (for example, from the time of signed informed consent up to but not including vaccine exposure) will be described in the medical history.

## **15.2 Collection, Documentation and Assessment of Adverse Events**

### **15.2.1 Unsolicited Adverse Events**

Participants will be provided and trained to use an electronic diary to make notes on unsolicited AEs up to D36 (Visit 4, see Section 15.3). Additionally, the Investigator will enquire about AEs during study visits. Clinically relevant laboratory parameter changes constitute unsolicited AEs, too, unless they are considered a symptom of an underlying AE or part of a syndrome that is reported as AE (e.g. presence of blood cells in urine in a person diagnosed

with urinary tract infection). In addition, symptoms noted during the symptom-driven physical exams (unless already covered by an AE) constitute AEs.

All unsolicited AEs need to be documented in the respective AE section of the eCRF during the applicable study visit (Visits 1 to 6 or unscheduled visit(s), if applicable), regardless of their source (AEs noted in the Participant diary [see Section 15.3], open question to Participant, laboratory parameters, symptom-driven physical examination). Serious adverse events will continue to be documented until the end of the study.

Any symptom is regarded as a separate AE. However, if the Investigator considers several symptoms to be in the context of one underlying diagnosis, the Investigator may merge these symptoms into one single appropriate AE. The AE term entered into the eCRF should contain all symptoms summarized to one event (e.g. 'Influenza with flu-like-symptoms, fever and headache').

The Investigator will follow-up each AE until it is resolved or until the medical condition of the Participant is stable. All relevant follow-up information will be reported to the Sponsor until the end of the study for each Participant. Serious adverse events ongoing at the time of Visit 8 will be followed until resolution or achievement of stable clinical conditions, latest until the overall end of the study.

**Beyond study end, SAEs that are fatal, life-threatening or suspected to be related to study treatment will be followed up to be reported until 6 months after the last study visit of the respective Participant.**

The following information will be documented for each AE: severity, causality, outcome, and seriousness, medically-attended, action taken to treat AE, action taken on IMP, start and stop dates.

Booster Phase:

Participants taking part in the Booster Phase will use the electronic diary to collect solicited AEs and make notes on unsolicited AEs occurring until Visit 10.

### 15.2.1.1 Severity

The Investigator will assess the severity of AEs using his/her clinical expertise and judgment based on the most appropriate description below:

**Mild (Grade 1):** Awareness of signs or symptoms, but easily tolerated, does not interfere with daily activities.

**Moderate (Grade 2):** Discomfort enough to interfere with usual activity and with or without requiring medical intervention.

**Severe (Grade 3):** Incapable of work or usual activity and requiring medical intervention.

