#### 10.6.2 During entire study period (including the Booster phase):

- **One** or more Participants experience an SAE or AESI with no likelier alternative cause than the study vaccine (i.e. possibly or probably related).
- **Two** or more Participants experience a Grade 3 systemic allergic reaction, e.g. generalized urticaria within 10 days after vaccine administration, or anaphylaxis within 24 hours following vaccine administration, with no likelier alternative cause than the study vaccine.
- **Three** or more Participants in the same dose group experience the same Grade 3iv solicited injection site reaction that (1) occurs within 7 days following vaccination and (2) lasts longer than 3 days.

---

iv **Note:** for the purpose of this study, AEs graded as potentially life threatening (Grade 4) will be reported as SAEs (see Section 16.1.2) and will thus fall under the first criterion in Section 11.6.

- **Three** or more Participants in the same dose group experience the same Grade 3 solicited systemic reaction that (1) occurs within 7 days following vaccination, (2) lasts longer than 3 days, and (3) has no likelier alternative cause than the study vaccine.
- **Three** or more Participants in the same dose group experience the same Grade 3 unsolicited AE, including Grade 3 laboratory abnormalities that are assessed to be clinically relevant by the Investigator, that (1) occurs within 36 days following first vaccination, and (2) has no likelier alternative cause than the study vaccine.

Grade 3 and Grade 4 solicited and unsolicited AEs will be confirmed with the site prior to stopping the study due to a pre-defined stopping rule. If any of the above-mentioned criteria is met or the DSMB recommends halting the study or discontinuing a dose group for other reasons (e.g. in response to an excess rate of AEs with the same suspected underlying pathological mechanism), the Sponsor will notify the appropriate regulatory authorities and EC according to local requirements.

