### 15.2.3 Solicited Adverse Events

Solicited AEs will be collected in the e-Diary by the Participant for 7 consecutive days after each vaccination, starting on the day of vaccination. They will be graded by the investigator

or the designee according to the FDA's Toxicity Grading Scale for Healthy Adult and Adolescent Volunteers Enrolled in Preventive Vaccine Clinical Trials, see Table 4, Table 5 and Table 6.

For solicited AEs which are serious and/or medically attended, the investigator carries out more detailed assessments are performed for unsolicited AEs (causality, outcome, action taken) and documents them in the eCRF. For solicited local and systemic AEs persisting beyond 6 days after vaccination, stop date is also documented in the eCRF (AE section).

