**Table 5 Grading of Systemic Reactions**

Vaccine-specific Criteria	Mild (Grade 1)	Moderate (Grade 2)	Severe (Grade 3)	Potentially Life Threatening (Grade 4) d
Nausea/vomiting	No interference with activity or one to two episodes/24 hours	Some interference with activity or > 2 episodes/24 hours	Prevents daily activity, requires outpatient IV hydration	Emergency room visit or hospitalisation for hypotensive shock
Headache	No interference with activity	Repeated use of non-narcotic pain reliever > 24 hours or some interference with activity	Significant; any use of narcotic pain reliever or prevents daily activity	Emergency room visit or hospitalisation
Fatigue	No interference with activity	Some interference with activity	Significant; prevents daily activity	Emergency room visit or hospitalisation
Myalgia	No interference with activity	Some interference with activity	Significant; prevents daily activity	Emergency room visit or hospitalisation

a Any Grade 4 systemic reaction will be reported as SAE, Grade 3 severity should be documented.

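### For clinical unsolicited adverse events, Protocol 15.2.1.1 requires both incapacity and medical intervention for Grade 3 and lists no Grade 4, so its severity wording leaves a gap and does not match Tables 4 to 6

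*Protocol*

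**What the plan says.** Protocol 15.2.1.1 defines three grades and stops there. Moderate (Grade 2) is "Discomfort enough to interfere with usual activity and with or without requiring medical intervention". Severe (Grade 3) is "Incapable of work or usual activity and requiring medical intervention". The investigator assigns the grade "using his/her clinical expertise and judgment based on the most appropriate description below".

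Solicited reactions have a separate scale. Under 15.2.3, "Solicited AEs will be collected in the e-Diary by the Participant for 7 consecutive days after each vaccination, starting on the day of vaccination", and they are graded by Tables 4 to 6, which have four levels. In Table 5, Grade 3 for fatigue and for myalgia is "Significant; prevents daily activity". Headache in Table 5 and injection-site pain in Table 4 also reach Grade 3 once daily activity is prevented. None of these four needs medical intervention.

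Grade 4 has a consequence of its own: under 15.1.2, "AEs graded as potentially life-threatening (Grade 4) (see Section 15.2.3 for solicited AEs) will be reported as SAEs". Footnotes to Tables 4 and 5 add that the severity of such a reaction is still written down as Grade 3.

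Four further places bear on the point:
- 15.2.2 sends every AE described in the eCRF to 15.2.1.1 for its severity and makes no exception for solicited AEs.
- 10.6.2 states that "Grade 3 and Grade 4 solicited and unsolicited AEs will be confirmed with the site" before the study is stopped under a predefined rule.
- 22.4 gives a four-grade laboratory scale. Its footnotes describe a Grade 4 unsolicited AE of low sodium and make Grade 4 laboratory values SAEs.
- 15.7 sends laboratory findings that 22.4 does not grade back to 15.2.1.1.

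**The concern.** Severity of unsolicited and of vaccine-related AEs is a secondary safety endpoint (Protocol 10.3.1.2). SAP 7.2.1 tabulates unsolicited AEs by maximum severity for the primary series and again for the booster phase. If the definition of severe leaves out events that incapacitate a participant without medical care, those tables understate severity. If investigators resolve the gap differently, the tables also mix two definitions of severe across sites.

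The same grades enter two operational criteria. One, in 10.6.2, applies when three or more participants in a dose group "experience the same Grade 3 unsolicited AE, including Grade 3 laboratory abnormalities" and further conditions are met. The other, in 11.6, withdraws an individual from further vaccination. Both depend on how Grade 3 is read.

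**Working it through.** No figure in the plan can be reproduced here, so the check is a comparison of texts.

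**Step 1. Is 15.2.1.1 exhaustive?** Cross functional effect with medical intervention:

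| | No intervention | Intervention |
|---|---|---|
| Activity interfered with | Grade 2 | Grade 2 |
| Activity prevented | no Grade 3 match; literally Grade 2 | Grade 3 |

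Grade 2 says explicitly that intervention does not matter. Grade 3 joins its two conditions with *and*. The lower-left cell is the gap.

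**Step 2. Same event, inside and outside the diary window.** The documents do not say outright how a listed reaction that starts after the window is graded. Reading 15.2.1 with 15.2.3, it becomes an unsolicited AE under 15.2.1.1. On that inference:

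| Event | Solicited (Tables 4 to 6) | Starting later (15.2.1.1) | What changes |
|---|---|---|---|
| Pain, headache, fatigue or myalgia preventing activity, no intervention | Grade 3, not an SAE on grade | Grade 2, read literally | One grade; SAE status unaffected |
| Nausea/vomiting preventing activity, outpatient IV hydration | Grade 3 | Grade 3 | Nothing |
| Headache, fatigue or myalgia, admitted to hospital | Grade 4, SAE, documented as Grade 3 | SAE under 15.1.2; Grade 3 if incapacitated | Nothing material |
| Headache, fatigue or myalgia, emergency room visit, not admitted | Grade 4, automatic SAE, documented as Grade 3 | At most Grade 3; SAE only if another 15.1.2 criterion is met | Automatic SAE trigger |
| Fever above 40.0°C | Grade 4, automatic SAE | No temperature cut-off | Automatic SAE trigger |
| Laboratory AE reaching Grade 4 in 22.4 | not applicable | Grade 4, SAE | Nothing |

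The loss of a grade and the loss of the automatic SAE trigger fall on different events.

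**Step 3. Do the cross-references agree?** 15.2.2 names 15.2.1.1 for every AE in the eCRF, while 15.2.3 names Tables 4 to 6 for solicited AEs. A solicited AE entered in the eCRF therefore has two severity definitions.

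**Step 4. Size.** Let r be the rate of incapacitating clinical unsolicited events and q the share that also receive medical intervention. Read literally, the rate recorded as Grade 3 is q × r. The documents give neither r nor q.

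To show direction only, take X ~ Binomial(50, p), one dose group, with rates assumed over a wide range and q assumed to be 1 or 0.5:

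| Assumed r | P(X ≥ 3), q = 1 (p = r) | P(X ≥ 3), q = 0.5 (p = r/2) |
|---|---|---|
| 2% | 0.078 | 0.014 |
| 4% | 0.323 | 0.078 |
| 6% | 0.584 | 0.189 |
| 10% | 0.888 | 0.459 |

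The sum leaves out the causality and time conditions of 10.6.2, so it is not an estimate of how often that criterion would be met.

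**The case against.** The strongest defence is that 15.2.1.1 is a best-fit scale. An investigator may judge that being unable to work fits the Grade 3 description better than discomfort that interferes with activity. That is a fair reading and softens the effect. It does not close the gap, because another investigator may follow the wording literally, and nothing in the protocol tells the two to agree.

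Three stronger readings are tempting and are not supported:

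- *That unsolicited AEs have no Grade 4.* Laboratory-based events graded under 22.4 do, and this can explain why 10.6.2 speaks of Grade 4 unsolicited AEs. The gap concerns clinical events.
- *That one event loses both its grade and its SAE status after the window.* Step 2 shows these are different events. Under Tables 4 and 5 a Grade 4 reaction is documented as Grade 3 in any case. Death, threat to life, hospitalisation, disability and medical importance make any AE serious under 15.1.2 whatever its grade or onset day, and AESIs are treated as SAEs.
- *That the suspension criterion is materially blunted, by an amount one can state.* The unsolicited Grade 3 criterion in 10.6.2 covers only 36 days from first vaccination, so it has little force in a booster phase 8 to 9 months after the primary series. The assumed rates have no source. The nearest observation (Protocol 8.5.1) is two subjects with severe solicited AEs by Day 36, which concerns other events and the other scale.

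It is also true that the SAP index tabulates severity separately for solicited reactions (Tables 14.2.1.4, 14.2.1.5, 14.2.1.26, 14.2.1.27) and unsolicited AEs (for example 14.2.1.15, 14.2.1.22, 14.2.1.39). No indexed severity table pools the two scales, and the primary safety endpoint is unaffected. What remains is the unsolicited severity tables themselves and the conflict between sections.

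**Conclusion.** The point holds as a defect of definition for clinical unsolicited AEs. In 15.2.1.1 an event that prevents work or usual activity without medical intervention has no matching Grade 3 description and reads literally as Grade 2, while Tables 4 and 5 treat comparable pain, headache, fatigue and myalgia as Grade 3. For listed reactions starting after the window, an emergency room visit without admission and fever above 40.0°C also lose the automatic SAE trigger, but not the other routes to seriousness. Sections 15.2.2 and 15.2.3 disagree on which scale governs solicited AEs in the eCRF.

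The consequence is possible under-counting of severe unsolicited AEs and inconsistent grading between sites in secondary safety tables. The direction is clear; the size cannot be estimated from the documents. The statements about late-starting reactions rest on the inference that 15.2.1.1 governs them, and the loss of a grade rests on a literal reading of a scale applied by judgement.

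**What to change.** 1. For severity documentation and tabulation, make Grade 3 in 15.2.1.1 exhaustive by aligning it with the functional criterion already in Tables 4 and 5: activity prevented, whether or not medical care was needed.
2. State whether Grade 4 applies to clinical unsolicited AEs and, if so, how it is documented, given the footnotes to Tables 4 and 5 that record such reactions as Grade 3.
3. State in SAP 7.2.1 which grades the maximum-severity tables use.
4. Say which scale applies to a listed reaction that starts after the diary window, and remove the conflict between 15.2.2 and 15.2.3.
5. Reconcile 15.2.1.1 with 15.1.2, 22.4 and the grade-based criteria in 10.6.2 and 11.6. Which suspension or withdrawal rule should apply is not for this review to decide; the sections need only agree.

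The cost is protocol and eCRF-guideline wording plus a line in the SAP. Somewhat more unsolicited AEs will be labelled severe. Because Part A has already been analysed, the amendment must state the date or study part from which the wording applies. Booster-phase AEs are tabulated separately, which makes a clean start there feasible.
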